2.1.2 Decision Rules to Proceed with Dose Expansion Phase

An interim analysis (IA) will be carried out when all subjects in the Dose Evaluation Phase in an individual tumor type have at least three months of treatment, or discontinued prematurely. This IA will be conducted independently for each tumor type. Investigator-assessed ORR will be used to guide the decision making for the Stage 2 portion of the study. However, all available efficacy and safety data will be used to select the recommended dose that will be further evaluated in the Dose Expansion Phase. Furthermore, if the level of efficacy observed at the recommended dose in the Dose Evaluation Phase does not warrant stopping evaluation of that tumor type, it will be used to select the appropriate Expansion Phase study design, either continuing with the second stage of a Simon 2-stage-like design or conducting a randomized Phase 2 study with comparative arm. The determination of low, moderate or high efficacy will be based primarily on the response rates observed with ulocuplumab and nivolumab (see [Table 2.1.2-1](#)), but the totality of available safety and efficacy data will be considered. For further information on the interim analysis and the efficacy thresholds used for decision rules, refer to [Section 7.5.1](#).

- If the number of responders per tumor type at the recommended dose level is consistent with low efficacy, the evaluation of that tumor type will be placed on hold pending final review of the data.
- If the number of responders per tumor type at the recommended dose level is consistent with moderate efficacy, the Dose Expansion Phase will continue with a single-arm evaluation.
- If the number of responders per tumor type at the recommended dose level is consistent with high efficacy, the Dose Expansion Phase will be continue with a randomized Phase 2 study with comparative arm.

Table 2.1.2-1: Stage 1 Efficacy Threshold For Each Tumor Type

Efficacy Threshold	SCLC	PAC
Low	3 responders / 19 subjects	1 responders / 21 subjects
Moderate	4-8 responders / 19 subjects	2-5 responders / 21 subjects
High	9 responders / 19 subjects	6 responders / 21 subjects

2.1.3 Dose Expansion Phase (Stage 2)

Based on the results of the IA, the Dose Expansion Phase will consist of a second stage of a Simon 2-stage single arm study (moderate efficacy) or a randomized Phase 2 study with comparative arm (high efficacy).

The second stage of a Simon 2-stage design will expand enrollment at the recommended dose level in a single arm study. The primary endpoint will be investigator-assessed ORR for both tumor types.

The randomized Phase 2 study will compare the combination therapy at the recommended dose level versus a comparative arm appropriate for that tumor type. The primary endpoint of this study will be dictated by the tumor type, where ORR is the endpoint for a randomized Phase 2 study in SCLC and OS for a randomized Phase 2 study in PAC. For ORR, independent radiology review committee (IRRC) will perform blinded independent review of the imaging per RECIST 1.1 criteria. Stratification factors will be used for this portion of the study and will include performance status (ECOG 0 vs. 1) and type of chemotherapy used in the first line setting (fluoropyrimidine-containing vs. gemcitabine-containing regimens). More details regarding the randomized Phase 2 for each tumor type are described in the protocol.

2.2 Treatment Assignment

A subject number will be assigned through an interactive voice response system (IVRS) once the subject has signed the informed consent form and is registered. Enrolled subjects that have met all eligibility criteria will continue with treatment assignment and drug vial assignment through the IVRS.

2.3 Blinding and Unblinding

Not applicable (open label study whatever the study phase).

2.4 Protocol Amendments

There are currently 5 approved amendments. The history of protocol amendments including the dates and changes to the protocol are summarized below.

- Amendment 1 (25-Mar-2015, all sites in the USA): The objective of this amendment was to initiate a biopsy sub-study that will allow to explore the changes in cellular architecture and localization of immune cell populations before and during treatment with ulocuplumab and nivolumab for use in future exploratory research (e.g., to validate the hypothesis that the refractory nature of SCLC and PAC results from an immunosuppressive environment surrounding the tumor that prevents activated lymphocytes from accessing the tumor site).
- Amendment 2 (20-May-2015, all sites): The objective of this amendment was to add a sentinel 400mg weekly ulocuplumab dose level in the dose evaluation phase at the request of regulatory authorities. It also incorporated administrative edits and minor clarifications to the study procedures.
- Amendment 3 (30-Sep-2015, all sites): This amendment changed dose delay, dose modification, discontinuation and DLT criteria to account for the known toxicity profiles of ulocuplumab and nivolumab and corrected internal inconsistencies in the management of toxicity. The major change was to remove the requirement to discontinue study therapy for > 7 days of grade 3 thrombocytopenia and replace it with a recommendation to delay therapy for > 7 days of grade 3 thrombocytopenia that occurs in the absence of bleeding. Discontinuation is still required for grade 4 thrombocytopenia lasting longer than 5 days.
- Amendment 4 (13-Jan-2016, all sites): This amendment changed DLT, dose delay, dose modification and dose discontinuation criteria to align with nivolumab program standard language. Additional changes have been made to platelet inclusion criteria and prohibited medications. Also, chest x-rays were added to monitor for potential early pulmonary toxicity.
- Amendment 5 (13-Jan-2016, all sites in the USA): The objective of this amendment was to add optional peripheral blood DNA sample to the biopsy sub study.

3 OBJECTIVES

3.1 Primary

- Stage 1: To identify the recommended dose and schedule, based on safety and efficacy, of ulocuplumab in combination with nivolumab in subjects with advanced or metastatic tumors.
- Stage 2: To evaluate the efficacy, separately by tumor type, based on objective response rate (ORR) or overall survival (OS; randomized Phase 2 study in PAC only), of ulocuplumab combined with nivolumab in subjects with advanced or metastatic tumors.

3.2 Secondary

- To assess the safety and tolerability of ulocuplumab combined with nivolumab, in subjects with advanced or metastatic tumors.

- To assess progression-free survival (PFS) with ulocuplumab combined with nivolumab, separately by tumor type, in subjects with advanced or metastatic tumors.

3.3 Exploratory

[REDACTED]

4 ENDPOINTS

Dose Evaluation Phase:

- DLT evaluation period: the primary endpoint (safety) is the incidence of DLTs.
- Dose Evaluation Phase: the primary endpoint is the investigator assessed ORR. Secondary endpoint is PFS.

Dose Expansion Phase:

- 2-stage design: the primary endpoint is the investigator assessed ORR. Secondary endpoint is PFS.

Common exploratory endpoints are duration of response, disease control rate, and the magnitude of reduction in tumor volume. For all tumor types and phases secondary endpoints will include the safety parameters as described in [Section 4.2](#).

Disease progression will primarily be determined using RECIST 1.1 criteria but “clinical progression” will be considered when RECIST 1.1 criteria cannot be evaluated and only clinical progression data is available (e.g., for some PAC subjects).

Timing of evaluation of the efficacy and safety endpoints is detailed in protocol Table 5.1-1 (Screening), 5.1-2 (On-Study Assessments for Dose Evaluation Phase, Stage 1: Ulocuplumab

Weekly Dosing), 5.1-4 (On-Study Assessments for Dose Expansion Phase, Stage 2) and 5.1-5 (Follow-up Assessments).

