### **8.3.2 Secondary Endpoint(s)**

Safety and tolerability will be analyzed through the incidence of DLTs, adverse events, serious adverse events, and specific laboratory abnormalities (worst grade). Toxicities will be graded using the NCI CTCAE version 4.0.

PFS is defined as the time from first dosing date (randomization date for the randomized Phase 2 study with comparative arm) to the date of the first documented tumor progression, as determined by the investigator (per RECIST 1.1), or death due to any cause, whichever occurs first. Subjects who die without a reported prior progression will be considered to have progressed on the date of their death. Subjects who did not progress or die will be censored on the date of their last evaluable tumor assessment. Subjects who did not have any on-study tumor assessments and did not die will be censored on the date of their first dosing date (randomization date for the randomized Phase 2 study with comparative arm). Subjects who started anti-cancer therapy without a prior reported progression will be censored on the date of their last evaluable tumor assessment prior to the initiation of subsequent anti-cancer therapy.

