#### **1.4.2.1 CT/MRI Scan**

CT/MRI is the best currently available and reproducible method to measure lesions selected for response assessment. Measurability of lesions on CT/MRI scan is based on the assumption that CT/MRI slice thickness is 5 mm or less. When CT scans have slice thickness greater than 5 mm, the minimum size for a measurable lesion should be twice the slice thickness.

Imaging-based evaluation is preferred to clinical examination. Helical (spiral) CT scans of the chest and abdomen are preferred. If not available, conventional (non helical, non spiral CT) should be used. If IV contrast is contraindicated, CT without contrast may be used, or MRI should be used at the Screening exam and at all TA time points. Subjects who develop contrast allergy after study enrollment must be followed by CT without contrast or MRI for subsequent tumor measurements.

Response and progression of disease must be documented by CT or MRI similar to the methods used at Screening.

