4.1.2 Secondary Endpoints

Progression-free survival is defined as the time from first dosing date to the date of the first documented tumor progression, as determined by the investigator, or death due to any cause, whichever occurs first. Subjects who die without a reported prior progression will be considered to have progressed on the date of their death. Subjects who did not progress or die will be censored on the date of their last evaluable (i.e., with non-missing tumor data) tumor assessment. Subjects who did not have any baseline or on-study tumor assessments and did not die will be censored on the date of their first dose. Subjects who started anti-cancer therapy without a prior reported progression will be censored on the date of their last evaluable tumor assessment prior to the initiation of subsequent anti-cancer therapy.

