7.5.3 Progression-free Survival

PFS will be estimated using KM methodology. Median values along with two-sided 95% CIs will be calculated. KM based PFS rates at 3, 6, 9, 12, and 18 months will be estimated and associated two-sided 95% CIs will be provided.

The following information will also be summarized:

- Number and type of events (progression: RECIST 1.1 or clinical, death),
- Number of subjects censored on first dosing date (number with no baseline tumor assessment and no death, number with no on-study tumor assessment and no death)

- Number of subjects censored on date of last tumor assessment on-study (number received subsequent anti-cancer therapy, still on-treatment, in follow-up, off study [lost to follow-up, withdraw consent, other]).

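### The SAP counts clinical-only progression as a PFS event, the protocol admits only RECIST 1.1 progression or death, and no PFS analysis by the protocol definition is planned

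*SAP*

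**What the plan says.** **Protocol.** Section 8.3.2 runs PFS to the "first documented tumor progression, as determined by the investigator (per RECIST 1.1), or death due to any cause". For everyone else the rule is "Subjects who did not progress or die will be censored on the date of their last evaluable tumor assessment"; with no on-study assessment and no death, censoring is at first dose. On later treatment it says: "Subjects who started anti-cancer therapy without a prior reported progression will be censored on the date of their last evaluable tumor assessment prior" to that therapy. Appendix 3, section 1.4.2.1, adds: "Response and progression of disease must be documented by CT or MRI similar to the methods used at Screening". Section 4.1 of that appendix calls a time point without imaging not evaluable, which is not the same as progressive disease.

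**SAP.** Section 4 determines progression primarily by RECIST 1.1, but clinical progression "will be considered when RECIST 1.1 criteria cannot be evaluated and only clinical progression data is available", with some pancreatic (PAC) subjects as its example. Section 4.1.2 defines PFS by the "first documented tumor progression, as determined by the investigator, or death due to any cause, whichever occurs first"; the protocol's RECIST qualifier is gone. Section 7.5.3 tabulates "Number and type of events (progression: RECIST 1.1 or clinical, death"), so clinical progression is an event type. Both 4.1.2 and 7.5.3 also keep censoring at first dose for subjects without tumor assessments who have not died.

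**The concern.** PFS is the only secondary efficacy endpoint that SAP 4 names for the Dose Evaluation Phase and the 2-stage design. The protocol already provides for subjects who cannot be scanned: they are censored, or they become events at death. The SAP therefore replaces a stated rule. The SAP's summary of the five amendments mentions no such change.

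The medians and landmark rates labeled PFS would then belong to a different endpoint from the protocol's. The SAP text supplied gives no criteria for clinical progression and no rule for dating it, in an open-label study where the treating investigator makes the call. The SAP's own example suggests that PAC will be affected more than small cell lung cancer (SCLC).

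**Working it through.** The documents attach no event target, power or alpha to PFS, so there is no stated figure to reproduce. The check is a comparison of rules, followed by an illustration of size.

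**Step 1. One subject, two rules.** Take a subject with clinical progression only: no RECIST 1.1 progression is ever recorded.

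| Later course | Protocol 8.3.2 | SAP 4, 4.1.2, 7.5.3 |
|---|---|---|
| Has on-study scans, starts new therapy | Censored at last evaluable assessment before it | Event at clinical progression |
| No new therapy, dies later | Event at death | Event at clinical progression |
| Alive, no new therapy, has on-study scans | Censored at last evaluable assessment | Event at clinical progression |
| Alive, no on-study scan | Censored at first dose | Event (SAP 4, and event types in 7.5.3), or censored at first dose (4.1.2, and censoring categories in 7.5.3) |

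In the first three rows the SAP gives an event where the protocol gives censoring or a later event. In the last row the SAP contradicts itself, and two programmers could derive different values. The SAP also leaves open whether the test that RECIST cannot be evaluated applies at the time of progression or to the subject's whole record.

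**Step 2. Size, on assumed inputs.** None of the following is a document figure except the scan interval, which is every 6 weeks for the first 24 weeks (protocol 5.4).

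- True time to progression T is exponential with median 2 or 3 months (mean = median / ln 2).
- A share of 10%, 20% or 30% has clinical-only progression.
- Other subjects progress at the next scan: T rounded up to a multiple of 6 / 4.345 = 1.38 months.
- SAP rule: a clinical-only subject is an event at T, with or without a scan.
- Protocol rule: a clinical-only subject who starts new therapy (0%, 50% or 100% of them) is censored at the last scan before T, or at time zero if there was none. Otherwise the event is death, at T plus an exponential time with median 2 months.
- Kaplan-Meier estimate, S(t) = product of (1 − d/n), with 200,000 simulated subjects per scenario.

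Three-month PFS, with ranges over the new-therapy fraction:

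| Median T | Clinical-only share | SAP rule | Protocol rule | Difference (points) |
|---|---|---|---|---|
| 2 months | 10% | 38.0–38.2% | 41.4–41.9% | 3.4–3.7 |
| 2 months | 20% | 37.6–37.7% | 44.8–45.2% | 7.2–7.5 |
| 2 months | 30% | 37.3–37.6% | 48.6–48.8% | 11.0–11.5 |
| 3 months | 10% | 52.5–52.7% | 55.5–55.8% | 2.8–3.2 |
| 3 months | 20% | 52.2–52.4% | 58.2–59.1% | 5.8–6.8 |
| 3 months | 30% | 51.8–52.1% | 60.8–62.5% | 8.8–10.7 |

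At a zero share the two rules agree exactly. The estimated median often does not move, because events cluster on the scan grid: it is 2.76 months under both rules in every 2-month scenario. The largest change is at a 3-month median and a 30% share, about 3.6 months (SAP) against 4.1 (protocol).

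**The case against.** The strongest reply is that the SAP rule is the better one. Subjects who deteriorate too far to be scanned are not a random subset, so censoring them is informative and tends to raise estimated PFS. Counting them as events lowers it, which is the cautious direction in a single-arm study. This stands as an argument about which version should lead. It does not excuse changing the endpoint without saying so, or leaving the dating rule and precedence open.

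The rule is also narrow. It applies only when RECIST cannot be evaluated and nothing but clinical data exists, so the whole endpoint is not replaced. Much is disclosed already: SAP 7.5.3 counts events by type, SAP 7.5 provides a PFS listing, and SAP 7.1 presents all analyses by tumor type. Those outputs show how many clinical events there were, but they do not give the protocol's PFS estimate.

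The SAP refers its conventions to a Data Presentation Plan that is not among the documents, so a definition or dating rule may exist there.

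Three stronger readings are tempting, and the documents do not support them.

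- *The response rate is affected.* SAP 4.1.1 also omits RECIST 1.1, so a reader might infer that clinical progression can end the best-response window. That section still requires progression to be objectively documented, and no effect on response rate is shown.
- *The shift is 10 to 20 points.* Dividing 2 to 4 reclassified PAC subjects by 21 gives 9.5% to 19%. That treats each of them as event-free at the landmark under the protocol rule. In fact they are censored, which Kaplan-Meier does not count as survival, or become events at death.
- *Error rates or go/no-go rules are compromised.* PFS is descriptive, and the numeric thresholds in protocol 8.5 and SAP 7.5.1 use response counts. PFS could enter only informally, through the review of all available data.

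**Conclusion.** The mismatch is real and should be corrected: followed as written, the SAP yields a secondary endpoint that differs from the protocol's, and for living subjects with no on-study scan it gives two answers. The effect is confined to clinical-only subjects. On the assumed inputs, 3-month PFS is about 3 to 4 points lower under the SAP rule at a 10% share and 6 to 8 points lower at 20%. The true share is unknown, so the actual shift could be negligible or larger.

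For scale, one standard error of a 45% rate in a Stage 1 PAC cohort of 21, ignoring censoring, is √(0.45 × 0.55 / 21) = 0.109, about 11 points. The shift is therefore modest beside sampling error, but it is systematic and runs in one direction. Alpha, power and the response-rate thresholds are unaffected. No conclusion about bias in a PAC-against-SCLC comparison follows, because none is planned.

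**What to change.** In SAP 4.1.2 and 7.5.3, report PFS by the protocol definition (RECIST 1.1 progression or death, with the protocol's censoring) as the protocol's secondary endpoint. Beside it, report PFS counting clinical progression as a labeled supportive analysis. For that version, state what qualifies as clinical progression, how it is dated, and whether it takes precedence over censoring at first dose when there is no on-study assessment.

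If the sponsor prefers the clinical version as the main one, the alternative is to amend protocol 8.3.2 accordingly and keep the RECIST-only curve as the sensitivity analysis. Either route removes the contradiction. SAP 4.1.1 on best overall response needs no change for this point.

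The cost is SAP wording and one additional Kaplan-Meier run (plus a protocol amendment under the alternative). The drawback is more censoring in the RECIST-only version, some of it possibly informative. Showing the two analyses together lets the reader see how much that matters.

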4.1 Efficacy Endpoints

4.1.1 Primary Endpoint

Investigator assessed ORR is defined as the number of subjects with a best overall response (BOR) of complete response (CR) or partial response (PR) divided by the number of treated subjects. The BOR is defined as the best response designation, as determined by the investigator, recorded between the first dosing date and the date of objectively documented progression or the date of subsequent anti-cancer therapy (systemic medication, surgery or radiotherapy for cancer), whichever occurs first. CR or PR determinations included in the BOR assessment must be confirmed by a second scan no less than 4 weeks after the criteria for response are first met. For subjects without documented progression or subsequent anti-cancer therapy, all available response designations will contribute to the BOR assessment. For subjects who continue treatment beyond progression, the BOR should be determined based on response designations recorded up to the time of the initial progression.

4.1.2 Secondary Endpoints

Progression-free survival is defined as the time from first dosing date to the date of the first documented tumor progression, as determined by the investigator, or death due to any cause, whichever occurs first. Subjects who die without a reported prior progression will be considered to have progressed on the date of their death. Subjects who did not progress or die will be censored on the date of their last evaluable (i.e., with non-missing tumor data) tumor assessment. Subjects who did not have any baseline or on-study tumor assessments and did not die will be censored on the date of their first dose. Subjects who started anti-cancer therapy without a prior reported progression will be censored on the date of their last evaluable tumor assessment prior to the initiation of subsequent anti-cancer therapy.

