## 4 RESPONSE CRITERIA (RECIST 1.1)

Table 4-1 provides a summary of the Time Point Response overall response status in subjects with Target and non-Target Disease

Table 4-1: Time Point Response - Subjects With Target ( ± Non-target) Disease			
Target Lesions	Non-Target Lesions	New Lesions	Overall Response
CR	CR	No	CR
CR	Non-CR/non-PD	No	PR
CR	Not evaluated	No	PR
PR	Non-PD or not all evaluated	No	PR
SD	Non-PD or not all evaluated	No	SD
Not all evaluated	Non-PD	No	NE
PD	Any	Yes or No	PD
Any	PD	Yes or No	PD
Any	Any	Yes	PD

CR = Complete Response, PR = Partial Response, SD = Stable Disease, PD = Progressive Disease, NE = Not Evaluable

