### 4.1 Missing Assessments and Not Evaluable Designation

When no imaging/measurement is done at all at a particular time point, the subject is **not evaluable (NE)** at that time point. If only a subset of lesion measurements are made at an

assessment, the case is also considered NE at that time point, unless a convincing argument can be made that the contribution of the individual missing lesion(s) would not have changed the assigned time point response.

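### The SAP's definition of an evaluable scan for PFS censoring is not aligned with the protocol's Not Evaluable designation, so an NE scan can set the censoring date

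*SAP*

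**What the plan says.** Protocol 8.3.2 gives the PFS rule: "Subjects who did not progress or die will be censored on the date of their last evaluable tumor assessment". It does not define evaluable there. It uses the same word for subjects who start other anti-cancer therapy before a reported progression.

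SAP 4.1.2 repeats the rule and adds a definition. Such subjects are "censored on the date of their last evaluable (i.e., with non-missing tumor data) tumor assessment". The sentence on subsequent therapy relies on the same term. Neither sentence mentions NE or the RECIST time-point response.

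Protocol Appendix 3, Section 4.1, makes a time point NE when no imaging is done. It then adds a second route, for scans at which some lesions go unmeasured: "the case is also considered NE at that time point". The section allows an exception where it can be argued convincingly that the missing lesions would have left the response unchanged. Table 4-1 in Appendix 3, Section 4, gives NE when target lesions are not all evaluated, non-target disease is not PD and there is no new lesion. It still gives PR or SD when the target response is PR or SD and the non-target status is "Non-PD or not all evaluated".

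Two other SAP passages matter. SAP 4.1.2 says: "Subjects who did not have any baseline or on-study tumor assessments and did not die will be censored on the date of their first dose". SAP 7.5.3 plans a table row headed "Number of subjects censored on date of last tumor assessment on-study", without the word evaluable.

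**The concern.** The SAP parenthesis works as a definition, and it tests whether data exist, not whether a response could be assigned. A scan with some target lesions measured and others not has tumor data, yet the protocol by default assigns it no response. If it is the subject's last scan, the subject stays in the risk set, event-free, up to a date at which the protocol does not recognise an assessment.

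At stake are the PFS median and the 3- to 18-month rates. The current SAP describes no randomized comparison, so no control arm would share and partly offset a shift. The situation is foreseeable: SAP Section 4 itself expects that RECIST 1.1 cannot be evaluated for some PAC subjects. PFS also belongs to the wider body of efficacy data that SAP 2.1.2 says will be considered alongside the response counts.

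**Working it through.** No figure in the plan depends on the PFS censoring date, so the first step compares the texts and the later steps illustrate direction and size.

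**1. The definitions side by side.** The SAP wording allows two readings: some tumor data are present (A), or none are missing (B). For scans that meet no PD criterion:

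| Scan | Appendix 3 | Reading A | Reading B |
|---|---|---|---|
| No imaging | NE | not evaluable | not evaluable |
| Some target lesions unmeasured, no convincing argument | NE | **evaluable** | not evaluable |
| Some target lesions unmeasured, convincing argument accepted | response assigned | evaluable | **not evaluable** |
| Target PR or SD, non-target not all evaluated | PR or SD | evaluable | **not evaluable** |
| Everything assessed | response assigned | evaluable | evaluable |

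Bold cells disagree with Appendix 3. Reading A, the plainer one, accepts an NE scan. Reading B rejects scans that Appendix 3 accepts. Neither reproduces Appendix 3.

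**2. Who is affected under reading A.** Only subjects with no RECIST progression, no clinical progression (an event under SAP Section 4 when RECIST cannot be evaluated) and no death, whose last scan before censoring or before subsequent therapy is NE. An NE scan followed by an evaluable scan, a progression or a death changes nothing.

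**3. Direction.** The Kaplan-Meier estimate is S(t) = ∏(1 − dᵢ/nᵢ) over event times tᵢ ≤ t. With events fixed, moving one censoring date from s to a later s′ adds 1 to nᵢ at every event time after s and up to s′. Each such factor rises. For example, with one event, 1 − 1/9 = 0.889 becomes 1 − 1/10 = 0.900. If no event falls in that interval, nothing changes. The shift is 6 weeks up to Week 24 and 12 weeks afterwards, and longer only if consecutive scans are NE.

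**4. Size, by simulation.** From the documents: the scan schedule (every 6 weeks to Week 24, then every 12) and sample sizes of 21, 41 and 44. Assumed, because the documents give no values: exponential PFS with median 3 months (13 weeks), 10% or 30% of subjects censored, and 10%, 30% or 100% of those with an NE last scan. There were 1,500 replicates per setting. Each entry is the mean of the estimate with the NE scan as censoring date minus the estimate with the preceding scheduled scan, for n = 21 / 41 / 44.

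| Censored | Last scan NE | 6-month PFS, points | Median, weeks |
|---|---|---|---|
| 10% | 10% | 0.13 / 0.13 / 0.12 | 0.09 / 0.08 / 0.06 |
| 10% | 30% | 0.39 / 0.41 / 0.41 | 0.32 / 0.26 / 0.22 |
| 30% | 10% | 0.38 / 0.40 / 0.41 | 0.29 / 0.22 / 0.30 |
| 30% | 30% | 1.24 / 1.23 / 1.26 | 0.79 / 0.76 / 0.77 |
| 10% | 100% | 1.31 / 1.40 / 1.36 | 1.01 / 0.78 / 0.60 |
| 30% | 100% | 4.38 / 4.31 / 4.40 | 2.56 / 2.38 / 2.51 |

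These are averages. In a single trial with n = 21 and 30% in both columns, the 95th percentile of the difference was 3.9 points. For scale, the assumed 3-month median implies a 6-month rate of 25%. Its binomial standard error is √(0.25 × 0.75 / 21) = 9.4 points at n = 21 and √(0.25 × 0.75 / 44) = 6.5 points at n = 44.

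**5. What does not move.** The two-stage designs rest on response counts. The rejection probability is Σ over x from r₁ to n₁ of P(X₁ = x) · P(X₂ ≥ r − x), where X₁ and X₂ are the binomial response counts in the two stages. SCLC (4/19, then 11/44) gives alpha 0.048 and power 0.905. PAC (2/21, then 5/41) gives alpha 0.046 and power 0.902. Both agree with the stated 5% and 90%, and neither uses PFS.

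**The case against.** The SAP never mentions partial scans, and its wording can be taken to mean complete data. On that reading it would not accept a scan with an unmeasured target lesion. This stands as far as it goes: the text is ambiguous and does not openly contradict the protocol. It does not rescue the definition, because the complete-data reading departs from Appendix 3 in the other direction (step 1), and two programmers could derive different dates.

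A reader might infer that every partial scan is NE, and so that subjects are counted as progression-free at scans that cannot show progression. The documents do not support that. Section 4.1 has its exception, Table 4-1 accepts incomplete non-target assessment, and a partial scan can still show PD through a new lesion or non-target progression. Clinical progression and death also count as events, so the affected group is narrow.

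A reader might also infer a material upward bias in PFS. Heavier assumptions do give larger figures. With 10–20% of subjects leaving at each scan and half of those last scans partial, 6-month PFS is about 2 to 4 points higher. With 20% leaving and every last scan partial, it is 37.5% against 28.3%. Nothing in the documents supports those rates, and the effect is near zero if NE last scans are rare.

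Finally, PFS is descriptive and the sampling error is far larger than the likely shift. Both points are correct and limit the importance of the issue. They do not justify leaving a one-directional choice open when a matching definition already exists in the protocol.

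**Conclusion.** The point holds as a misaligned definition with a small, one-directional effect. Under the plain reading of SAP 4.1.2, a scan that Appendix 3 designates NE can set the PFS censoring date, and the PFS estimate then stays the same or rises.

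On the assumptions in step 4, the average effect on 6-month PFS is about 0.1 to 1.3 points with 10–30% NE last scans among censored subjects, and 1.3 to 4.4 points if all of them were NE. The corresponding shifts in the median are about 0.1 to 0.8 weeks and 0.6 to 2.6 weeks. The direction follows from the estimator, but the size rests entirely on assumed PFS, censoring and NE rates. An actual overstatement is possible, not shown. No hypothesis test, sample size or numerical Stage 2 threshold is affected.

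A gap accompanies it. The SAP's first-dose rule covers subjects without assessments, and no rule clearly covers a subject who was scanned on study but whose scans were all NE.

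**What to change.** Make three edits before database lock.

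1. In SAP 4.1.2, replace the parenthesis after evaluable with: *(i.e., with an investigator time-point response other than NE under Protocol Appendix 3, Section 4)*. State that it applies to both censoring sentences, the general one and the one on subsequent anti-cancer therapy. Because it uses the assigned response, it keeps the convincing-argument exception and the Table 4-1 allowance for incomplete non-target assessment.
2. In SAP 7.5.3, use the same term, so that the censoring table counts subjects at their last evaluable on-study assessment.
3. In SAP 4.1.2, state that subjects with no evaluable on-study assessment who did not progress or die are censored at first dose, and count them under first-dose censoring in SAP 7.5.3.

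The cost is a few words in the SAP and one programming condition on the time-point response. The reported PFS may become slightly less favourable.
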